#### b. Sample

##### Inclusion criteria:

- Age > 18
- Patients presenting for elective hernia repair, with VHWG grade 2 or above
- Patients deemed to be good surgical candidates, with **no active life-threatening** cardiac disease, pulmonary disease, renal disease, hematologic disease
- Patients presenting for resection of large abdominal wall tumors who are expected to undergo have tumor extirpative defect that would require biologic mesh for closure

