##### Sample size (power analysis)

Our primary outcome is hernia recurrence rate at 30 days and 1 year postoperatively.

According to two industry-sponsored studies, the rate of hernia recurrence with XenMatrix is approximately 7%.

According to the large series by Clemens *et al*, the rate of hernia recurrence with Strattec is approximately 2.9%.

Assuming an alpha error of 5%, a power of 80%, and assuming a large standard deviation (3), the number of patients in each group that is needed to demonstrate a significant difference is 5.

In order to adequately power the study to analyze the secondary outcomes, **we plan to enroll 35 patients in each group (70 patients total)**

*a. Detailed study procedures*

When a patient with a ventral hernia or an abdominal wall tumor presents to the senior author for evaluation for abdominal wall reconstruction, a full history and physical examination will be performed. Patient who satisfy the study inclusion and exclusion criteria will be offered the opportunity to participate in the study. If they agree to participate, informed consent and HIPAA forms will be filled out and signed.

Patients will then be randomized to group A (Strattice) or group B (XenMatrix) using a random number generator made in Microsoft Excel. They will not be told which group they are in, and only the principal investigator, co-investigators and operating room staff will be aware of which mesh is being used.

The patients will be asked to fill out 4 surveys preoperatively: PROMIS Pain Intensity survey, PROMIS Pain Interference survey, PROMIS physical function survey and HerQLes survey.

They will then undergo surgery, and will be followed weekly for a month, then every 3 months for a year, and as needed. They will be evaluated for hernia recurrence, bulge, or other SSOs throughout the follow-up period.

They will be asked to fill out the PROMIS Pain Intensity survey, PROMIS Pain Interference survey, PROMIS physical function survey and HerQLes survey at 1 year.

*c. Measurements*

*The patient characteristics that will be collected will include:*

- 1) Age
- 2) Comorbidities
  - a. Diabetes
    - i. Hemoglobin A1c
  - b. Current tobacco use (defined as <4 weeks prior to surgery)
  - c. Former tobacco use (defined as >4 weeks prior to surgery)
  - d. Chronic Obstructive Pulmonary Disease
  - e. Coronary Artery Disease
  - f. Malnutrition (defined as prealbumin < 18 or albumin < 3.5)
  - g. Corticosteroid use

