  - h. Use of other immunosuppressants
  - i. BMI
  - j. History of chemotherapy
  - k. History of radiation to abdomen
- 3) Hernia characteristics
  - a. Size on abdominal CT scan in cm^2
  - b. Ventral Hernia Working Group (VHWG) grade

- i. Grade 1 (low risk): no comorbidities, no history of wound infection, no contamination
- ii. Grade 2 (comorbid): smoker/obese/diabetic/immunosuppressed/COPD
- iii. Grade 3 (potentially contaminated): previous wound infection, stoma present, GI tract violated
- iv. Grade 4 (infected): infected mesh, septic dehiscence
- c. Number of prior hernia repairs

*The surgical details that will be collected will include*

- 1) Surgeon
- 2) Date of surgery
- 3) Wound class
  - a. Class I = clean
  - b. Class II = clean-contaminated
  - c. Class III = contaminated
  - d. Class IV = dirty
- 4) Whether bowel resection performed
- 5) Whether component separation technique (CST) performed
  - a. If yes, standard CST versus minimally-invasive CST
- 6) Whether fascia able to be primarily closed
- 7) Type of mesh used
- 8) Location of mesh
  - a. Overlay (superficial to the primary fascial repair)
  - b. Underlay (deep to the primary fascial repair)
    - i. Sub-rectus
    - ii. Intraperitoneal

*The outcome data that will be collected will include*

- a. Hernia recurrence
- b. Bulge
- c. SSOs
  - a. Infection
  - b. Seroma
  - c. Hematoma
  - d. Wound dehiscence
  - e. Skin necrosis
  - f. Formation of enterocutaneous fistula
  - g. Mesh infection
- d. Score on PROMIS Pain Intensity survey
- e. Score on PROMIS Pain Interference survey
- f. Score on PROMIS Physical Function
- g. Score on HerQLes survey

*d. Internal validity*

Since this is a randomized-controlled trial, we expect the baseline demographics and patient characteristics to be similar between the two groups, and we expect our results to be internally valid.

*e. External validity*

The study results will reflect the outcomes within our study population at the Ohio State University Medical Center, and may not be generalizable to other institutions.

*f. Data analysis*

Baseline patient characteristics will be compared between the two groups to ensure that the two groups are similar and that there are no confounders

Multiple binary logistic regression will be performed to detect predictors of hernia recurrence, bulge and other SSOs. It will also be used to determine whether one mesh has a higher rate of complications compared to the other.

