SSO within 6 weeks was analyzed using logistic regression. Separate logistic regression models were fit for the RCT and for the observational cohort, with mesh type (XenMatrix vs. Strattice) as the primary predictor. Simple logistic regression and multivariable logistic regression was used for each study type (RCT and observational). Both models were adjusted by hernia width, CDC wound class, immunosuppression, and recurrent hernia to account for potential confounding in the observational group. Covariates were selected based on evidence in the literature as well as potential imbalance. The final number of covariates was limited to avoid model overfitting.

Confounders:

- Hernia width
- Wound class
- Immunosuppression
- Recurrent hernia

After obtaining separate estimates from the RCT and observational cohort, a random-effects meta-analysis was performed to derive a combined estimate. A combined estimate for the log odds ratio was calculated using inverse variance weighting and a restricted maximum likelihood estimator. Between-study heterogeneity was assessed by the I^2 measure.

Forest plots and summary tables for the log odds ratio and odds ratio were generated to summarize results.

Statistical and Study Design Considerations

Rationale for Combining RCT and Observational Study Data

- RCT was terminated early for difficulties with enrollment, resulting in very imbalanced group sizes.
- While some guidelines caution against combining observational studies with RCTs in a single meta-analysis due to methodological differences [2], other sources emphasize that in many situations, the benefits of incorporating all available evidence can outweigh the drawbacks, provided proper methods are used [2, 3]
- [3] proves a framework for synthesis of non-randomized and randomized studies.
 - In this study, the observational data come from the same single site as the RCT and are not subject to publication bias.

Choice of Statistical Methods

- Frequentist methods were chosen for broader audience familiarity. Although Bayesian multi-level models are an option, they can be sensitive to prior specification, and the intended audience may be less familiar with them.
- There are not enough events to perform analysis for other outcomes.
- Propensity score matching was not used because it can substantially reduce the sample size (i.e., discarding unmatched patients).

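### The adjusted RCT odds ratio conditions on CDC wound class, which is recorded at surgery, after randomisation, by a team that knows the mesh, so randomisation alone does not protect it from bias

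*SAP*

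**What the plan says.** SAP, Primary Outcome Analysis: "Separate logistic regression models were fit for the RCT and for the observational cohort", each first with mesh alone and then with covariates. On the covariates: "Both models were adjusted by hernia width, CDC wound class, immunosuppression, and recurrent hernia to account for potential confounding in the observational group". Under Additional comments the SAP gives a second reason, that in a small trial randomisation may leave the arms unbalanced.

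The protocol fixes the order of events (Detailed study procedures). After consent: "Patients will then be randomized to group A (Strattice) or group B (XenMatrix) using a random number generator made in Microsoft Excel". After the baseline surveys: "They will then undergo surgery, and will be followed weekly for a month". On who knows the mesh: "only the principal investigator, co-investigators and operating room staff will be aware of which mesh is being used". Research design (III.a) confirms that surgeons are not blinded.

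In protocol III.c, wound class is not among the patient or hernia characteristics. It is item 3 of the list introduced by "The surgical details that will be collected will include", next to bowel resection, component separation and fascial closure. The SAP also tabulates it under surgical characteristics (Tables 2a and 2b).

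The SAP's Executive Summary takes the change from a non-significant unadjusted pooled estimate to a significant adjusted one as a sign that the unadjusted analysis may have been confounded.

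**The concern.** In a randomised comparison, adjusting for a variable fixed before allocation is safe, because allocation cannot have influenced it. A variable recorded afterwards has no such guarantee. If the mesh, or the team's knowledge of it, changes how the operation is done or how its contamination is classified, patients in the same wound class are no longer comparable between arms, and adjustment can create or remove a mesh difference.

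Neither of the SAP's reasons covers this. Confounding in the observational cohort is no reason to put wound class in the separate RCT model. Chance imbalance is a sound reason to adjust a small trial, but only for variables fixed before allocation.

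The RCT estimate carries about 59% of the weight in the adjusted pooled odds ratio, which is the SAP's only statistically significant pooled result.

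**Working it through.** **1. The plan's unadjusted RCT figure.** From SAP Table 3a, SSO within 6 weeks occurred in 1/16 Strattice and 11/30 XenMatrix patients.

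- OR = (11 × 15)/(19 × 1) = 8.684; log OR = 2.162.
- SE = √(1/11 + 1/19 + 1/1 + 1/15) = 1.100; z = 1.965; P = 0.049.
- The profile-likelihood interval on the log scale is 0.365 to 5.123.

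All match the SAP. The unadjusted pool also reproduces: 3.718 (0.897 to 15.404), P = 0.070.

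**2. The plan's adjusted pool.** The adjusted models cannot be refitted without patient data, so standard errors are taken back from the stated log OR and P.

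- RCT: log OR 2.968, P = 0.023, so SE = 2.968/2.273 = 1.306.
- Observational: log OR 1.882, P = 0.230, so SE = 1.882/1.200 = 1.568.
- Inverse-variance weights: 1/1.306² = 0.587 and 1/1.568² = 0.407. The RCT share is 0.587/0.994 = 59%.
- Pooled log OR = 0.59 × 2.968 + 0.41 × 1.882 = 2.523, so OR 12.47 (1.75 to 89.1), P = 0.012, Q = 0.283.

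This agrees with the stated 12.476 (1.745 to 89.199) within rounding.

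**3. Replacing only the RCT estimate.** Use the unadjusted RCT value (2.162, SE 1.100) with the adjusted observational value (1.882, SE 1.568).

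- Weights 0.826 and 0.407; RCT share 67%.
- Pooled log OR = 0.67 × 2.162 + 0.33 × 1.882 = 2.069; SE = 1/√1.233 = 0.901. Q = 0.021, so the between-study variance is zero.
- OR = 7.92 (1.36 to 46.3), P = 0.022.

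This removes all four RCT covariates, not wound class alone. It indicates scale and does not replace the refit.

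**4. What wound class alone could do.** Table 2a gives classes 1/2/3/4 as 7/5/2/2 of 16 for Strattice and 17/4/2/7 of 30 for XenMatrix (χ² = 3.08 on 3 df, P = 0.38). The SAP does not cross SSO with wound class. Every possible placing of the 1 + 11 events over these margins was therefore enumerated, and SSO was regressed on mesh and wound class.

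| Coding of wound class | Range of the RCT odds ratio for mesh |
|---|---|
| 1 vs 2–4 | 8.2 to 44 |
| 1–2 vs 3–4 | 8.6 to no finite estimate |
| Four levels | 6.7 to 54.6, in the 394 of 464 placings with a finite estimate |

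The published figures are compatible with wound class contributing almost nothing to the move from 8.68 to 19.46, or more than all of it.

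**5. Sparseness.** With mesh, linear width, immunosuppression and recurrent hernia, wound class makes 5 slopes (linear) or 7 (categorical). The 12 RCT events give 12/5 = 2.4 or 12/7 = 1.7 events per slope.

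**6. A second post-allocation input.** The SAP substitutes mesh size where hernia size is missing. In Table 1a, width rises from N = 25 to 30 for XenMatrix and stays at 16 for Strattice, so all five RCT substitutions are in one arm. The means imply that the five values average (30 × 13.06 − 25 × 11.67)/5 = 20.0, against 11.67 for the measured widths. The size of the mesh used describes the operation and belongs to the allocated product.

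**The case against.** **Bias is possible but not shown.** Patients are still compared by randomised mesh. A reader might infer that the adjusted result is no longer a randomised comparison at all. The documents do not support that. Bias requires allocation, or knowledge of it, to alter the class or its recording. No section says that it does, or says who assigned the class and when. The arms do not differ detectably on wound class (P = 0.38), although with 46 patients this is weak reassurance. The unadjusted RCT result is reported beside the adjusted one. This objection stands against the strong reading. It does not make wound class a pre-allocation variable.

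**The shift has other explanations.** A reader might also put the rise from 8.7 to 19.5 down to wound class. Three other covariates entered together with it (immunosuppression is 2/16 vs 10/30), there is one Strattice event, and odds ratios move on adjustment even without confounding. This stands. It equally undermines the SAP's reading of the shift as confounding among randomised patients.

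**VHWG grade is not a ready substitute.** It is an entry criterion ("Patients presenting for elective hernia repair, with VHWG grade 2 or above"), but the protocol's grade 3 includes a breach of the gastrointestinal tract, which can happen at operation. The SAP tabulates the grade with the surgical characteristics, and two RCT patients have grade 1. They may have entered through the tumour-resection criterion, so this is not proof of regrading, but nothing shows that the tabulated grade is the screening value. Nor does wound class show a distinct imbalance: class 4 and VHWG grade 4 are both 2/16 vs 7/30.

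**Protocol III.f.** It says of its regression: "It will also be used to determine whether one mesh has a higher rate of complications compared to the other". A reader might infer that closure, bridging and mesh plane are adjusted for there. III.f names no covariates, and the SAP model contains none of these three.

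**Pooling and hindsight.** Changing only the RCT covariates would pool log odds ratios that condition on different sets, and the results are already known. Both points stand. They call for showing each version and choosing the lead by when covariates were fixed, not by the result.

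**Conclusion.** The point holds in a limited form. The adjusted RCT odds ratio of 19.458 conditions on a covariate recorded after allocation by an unblinded team, and the SAP does not discuss this. Randomisation does not protect the estimate if allocation, or knowledge of it, affects the class or its recording. Whether that happened cannot be told from the documents. Among randomised patients, the shift on adjustment should not be presented as evidence of confounding.

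The share of the shift due to wound class is unknown. Dropping RCT adjustment altogether while keeping the observational adjustment lowers the pooled odds ratio from 12.476 to about 7.9, and P moves from 0.012 to 0.022. On that comparison the size changes materially and nominal significance does not. With both sources unadjusted, P is 0.070. These figures rest on standard errors recovered from rounded P values. An odds ratio adjusted only for pre-randomisation variables cannot be computed without patient data.

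**What to change.** - In the RCT model, adjust only for variables fixed before randomisation: immunosuppression, recurrent hernia and preoperatively measured hernia width.
- Do not use the mesh-size proxy in that model. Recover the five widths from preoperative records if possible. Otherwise impute them from preoperative variables or leave width out. A complete-case fit would drop five patients, all XenMatrix.
- Lead the RCT and pooled results with that estimate or the unadjusted one. Report the model with wound class as a labelled sensitivity analysis.
- Use VHWG grade only if the value assigned before randomisation is available.
- Keep wound class in the observational model. State that the two log odds ratios then condition on different covariates, or also show the pool with a common preoperative set.
- In the Executive Summary, remove the confounding interpretation for the randomised patients.
- If the protocol III.f regression is used to estimate the mesh effect, state that it excludes intraoperative variables.

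The cost is SAP wording and one refit with its pooled result. The model may explain slightly less outcome variation. If wound class was entered as categorical, removing it also frees three slopes in a model with 12 events.

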SSO within 6 weeks : Yes	20	4/12 (33.33)	4/8 (50.00)	$\chi^2_1=0.56, P=0.46^2$
SSO Type (cata)				
Skin necrosis : Yes	20	0/12 (0.00)	1/8 (12.50)	$\chi^2_1=1.58, P=0.21^2$
Enterocutaneous fistula : Yes	20	2/12 (16.67)	0/8 (0.00)	$\chi^2_1=1.48, P=0.22^2$

Table 3b: 6-week outcomes, observational patients (*continued*)

Variables	N	Strattice	XenMatrix	Test Statistic
Dehiscence : Yes	20	2/12 (16.67)	0/8 (0.00)	$\chi^2_1=1.48$, P=0.22 ²
Seroma : Yes	20	1/12 (8.33)	0/8 (0.00)	$\chi^2_1=0.70$, P=0.40 ²
Hematoma : Yes	20	0/12 (0.00)	0/8 (0.00)	NA
Infection : Yes	20	1/12 (8.33)	3/8 (37.50)	$\chi^2_1=2.55$, P=0.11 ²
Mesh infection : Yes	19	0/11 (0.00)	0/8 (0.00)	NA

Note:

N is the number of non-missing value. 1 Kruskal-Wallis. 2 Pearson. 3 Wilcoxon.

Stat, P is the test statistic and p-value.

cata = check all that apply

Results

Executive Summary

Unadjusted Random Effects Meta-Analysis (Simple Logistic Regression):

Effect Estimate (Odds Ratio): 3.718 (0.897, 15.404)

Significance: The pooled estimate was not statistically significant.

Heterogeneity:

I^2 (total heterogeneity / total variability): 3.29%

H^2 (total variability / sampling variability): 1.03

Test for Heterogeneity:

$Q(df = 1) = 1.0340$, $p\text{-val} = 0.3092$

There appears to be minimal variability between the two studies. The I^2 value of 3.29% indicates that nearly all of the total variation can be explained by chance rather than true heterogeneity, and an H^2 of 1.03 reflects low excess variability. The Q test ($Q = 1.034$, $p = 0.3092$) is nonsignificant, confirming that there is no strong evidence of meaningful heterogeneity.

Adjusted Random Effects Meta-Analysis (Multivariable Logistic Regression):

Effect Estimate (Odds Ratio): 12.476 (1.745, 89.199)

Significance: The pooled estimate was statistically significant.

Heterogeneity:

I^2 (total heterogeneity / total variability): 0.00%

H^2 (total variability / sampling variability): 1.00

Test for Heterogeneity: $Q(df = 1) = 0.2830$, $p\text{-val} = 0.5947$

There is effectively no evidence of meaningful heterogeneity between the RCT and the observational study, provided by 0.00% I^2 value. Similarly, $H^2 = 1.00$ supports the absence of excess variability beyond what would be expected by sampling error alone. Finally, the Q test ($Q = 0.2830$, $p = 0.5947$) is non-significant, confirming that the studies are consistent and do not exhibit statistically detectable heterogeneity.

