When covariates were included in the model, a previously non-significant association between the exposure and outcome became statistically significant. This shift suggests that the unadjusted analysis may have been confounded—i.e., certain variables were masking or biasing the relationship.

Note

Be wary of exaggerated findings, as smaller studies are more prone to exaggeration. This is known as a Type M (magnitude) error. In other words, a finding must be large enough to exceed the statistical significance threshold despite wide confidence intervals, which systematically inflates the estimated effect size. Consequently, although we observed a strong effect, its true magnitude may be substantially lower than our point estimate suggests.

Gelman, A., & Carlin, J. (2014). Beyond Power Calculations: Assessing Type S (Sign) and Type M (Magnitude) Errors. *Perspectives on Psychological Science*, 9(6), 641-651.

[figure not shown]
Random Effects Meta-Analysis: Simple Logistic Regression

Simple logistic regression = logistic regression with no adjustment for confounders

[figure not shown]
Random Effects Meta-Analysis: Simple Logistic Regression

Study	Estimate (log OR)	95% CI (log OR)	Estimate (OR)	95% CI (OR)	P-value
Randomized	2.162	(0.365, 5.123)	8.684	(1.441, 167.853)	0.049
Observational	0.693	(-1.143, 2.597)	2.000	(0.319, 13.423)	0.459
RE Meta-Analysis	1.313	(-0.108, 2.735)	3.718	(0.897, 15.404)	0.070

Forest Plot: Log Odds Scale

Forest Plot: Odds Scale

[figure not shown]

Random Effects Meta-Analysis: Multivariable logistic regression

[figure not shown]
Random Effects Meta-Analysis: Multivariable Logistic Regression

Study	Estimate (log OR)	95% CI (log OR)	Estimate (OR)	95% CI (OR)	P-value
Randomized	2.968	(0.815, 6.261)	19.458	(2.258, 523.717)	0.023
Observational	1.882	(-0.898, 5.783)	6.569	(0.407, 324.629)	0.230
RE Meta-Analysis	2.524	(0.557, 4.491)	12.476	(1.745, 89.199)	0.012

Log Odds Scale

Odds Scale

FAQ

Q: What is overfitting?

A: Overfitting in regression happens when a model is too complex, often due to too many parameters relative to a small sample size, causing it to capture noise rather than the true data pattern. With limited data, the model lacks sufficient information to generalize well, leading to poor performance on new data because it is overly tailored to the specific quirks of the training set.

Q: What is a chunk (or composite) test?

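### The adjusted SSO models fit 5 to 7 slopes to 12 and to 8 events: the size of the pooled odds ratio of 12.5 is unreliable, and the move from p=0.070 to p=0.012 is not evidence of confounding

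*SAP*

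**What the plan says.** SAP, Primary Outcome Analysis: logistic models for SSO within 6 weeks are fitted separately in the randomised and observational patients, unadjusted and adjusted. On adjustment: "Both models were adjusted by hernia width, CDC wound class, immunosuppression, and recurrent hernia to account for potential confounding in the observational group". It continues: "The final number of covariates was limited to avoid model overfitting". The coding of the four-level wound class is not given, and no penalised or exact method is named.

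SAP, Choice of Statistical Methods, on the remaining endpoints: "There are not enough events to perform analysis for other outcomes".

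SAP, Executive Summary and results tables: the pooled odds ratio is 3.718 (0.897 to 15.404), p=0.070 unadjusted, and 12.476 (1.745 to 89.199), p=0.012 adjusted. The adjusted interval for the randomised patients is "2.258, 523.717". The summary observes that "a previously non-significant association between the exposure and outcome became statistically significant" and comments: "This shift suggests that the unadjusted analysis may have been confounded".

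SAP, FAQ, describes overfitting as "often due to too many parameters relative to a small sample size".

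The SAP also warns, under Additional comments and in the Note after the summary, that estimates from small studies tend to be exaggerated (Type M error).

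**The concern.** The only statistically significant pooled result rests on two maximum-likelihood models with between one and two and a half events per slope. By the SAP's own description this is an overfitting setting, yet the text says that the covariate count was held down to avoid it.

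The SAP then offers one explanation for the move across p=0.05: that the unadjusted analysis may have been confounded. In the randomised patients the odds ratio also rose, from 8.7 to 19.5, and there only chance imbalance can confound. A reader could take 12.5 as the better estimate because confounding has been dealt with, when neither the size nor the reason is established.

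**Working it through.** **Inputs.** SSO events (Tables 3a, 3b): randomised 1/16 Strattice and 11/30 XenMatrix, 12 in 46; observational 4/12 and 4/8, 8 in 20. Slopes: mesh 1, hernia width 1 (if linear), wound class 1 (ordinal) to 3 (categorical), immunosuppression 1, recurrent hernia 1, so 5 to 7.

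**Reproducing the unadjusted result.**
- Randomised: log OR = ln[(11×15)/(19×1)] = 2.162; SE = √(1/11+1/19+1/1+1/15) = 1.100; OR 8.684, p=0.049.
- Observational: log OR = ln[(4×8)/(4×4)] = 0.693; SE = √(1/4+1/4+1/4+1/8) = 0.935; OR 2.000, p=0.459.
- REML pooling (τ²=0.035): log OR 1.313, SE 0.725, OR 3.718 (0.897 to 15.405), p=0.070. This matches the SAP.

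**Reproducing the adjusted result.** SE = estimate / z from the reported p-values: 2.968/2.273 = 1.306 and 1.882/1.200 = 1.568. Inverse-variance pooling (τ²=0) gives 2.523, OR 12.47 (1.75 to 89.1), p=0.012. This also matches. The arithmetic is right; the question is what it means.

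**Events per slope.** Randomised: 12/5 = 2.4 to 12/7 = 1.7. Observational: 8/5 = 1.6 to 8/7 = 1.1. In the observational patients, immunosuppression (4/12 vs 0/8) and wound class 4 (3/12 vs 0/8) occur only with Strattice, and class 3 is one patient (Tables 1b, 2b).

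**Variance and weights.** Adjustment multiplies the variance of the log OR by 1.306²/1.100² = 1.41 (randomised) and 1.568²/0.935² = 2.81 (observational). The randomised weight rises from 42% to 59%. Applying the adjusted weights to the unadjusted estimates: 0.5905×2.162 + 0.4095×0.693 = 1.560, OR 4.76. Re-weighting alone is therefore (1.560−1.313)/(2.524−1.313) = 20% of the log-OR shift.

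**What the method does when there is nothing to confound.** Mesh-by-SSO counts were held at the reported values, and covariates were shuffled within arm at their tabled margins, so they were unrelated to SSO. Assumptions: recurrent hernia is the tabled previous repair; imputed width is drawn from the tabled mean and SD, clipped to the range; covariates are independent within arm. There were four scenarios (width normal or lognormal; wound class linear or class 1 vs 2–4) of 3,000 datasets each.

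| Fit | Median pooled OR | p<0.05 | OR ≥12.5 |
|---|---|---|---|
| Maximum likelihood, four covariates | 5.5–5.9 (5th–95th percentile about 2.7–15) | 46–50% | 6–9% |
| Maximum likelihood, two covariates (width; class 1 vs 2–4) | 4.3 | 34–35% | about 1% |
| Firth, four covariates | 3.7–3.9 | – | under 0.5% |

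In the four-covariate maximum-likelihood runs, 17–20% of datasets were excluded because a fit diverged, mostly in the observational patients.

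**Non-collapsibility.** With covariates independent of mesh, a conditional OR of 12.5 corresponds to a marginal OR of 9.5, 7.6, 5.2 or 3.9 for assumed covariate log-odds effects of 0.7, 1.0, 1.5 or 2.0. Strong predictors alone could open the gap.

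**Selection by significance.** At the adjusted pooled SE of 1.00, only an OR of at least exp(1.96×1.0036) = 7.15 reaches p<0.05. If the true OR were 3.7, power would be 26% and the median significant estimate 11.6.

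**Randomised patients, unadjusted.** Fisher p=0.035. Firth (0.5 added per cell): (11.5×15.5)/(19.5×1.5) = 6.09, penalised-profile interval 1.23 to 60.6, p=0.025. The Wald interval for the same estimate is 0.98 to 37.9, p=0.053. The Firth unadjusted pooled OR is 3.29 (0.94 to 11.6).

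**The case against.** - **The SAP already warns about size.** The Type M note says that the true effect may be substantially smaller, and the wide intervals are printed. That stands as a general caution. It is not tied to the number of covariates, and it sits beside an overfitting assurance and a confounding explanation that pull the other way.
- **The wording is guarded.** The covariate sentence says only that the number was limited, and four is fewer than the tables would allow. The confounding sentence is hedged. Both are fair readings. But limiting to four left the models in the range the sentence says it avoids, and confounding is the only explanation offered.
- **The shuffling result explains only part of the size.** A median of 5.5 to 5.9 covers about a third of the log-OR shift. For the randomised patients alone the median is about 10, with 19.5 or more in only 6%. The share below 0.05 is high partly because the unadjusted p is already 0.070. The 7-slope coding was not run. This stands: real covariate effects or chance imbalance (immunosuppression 2/16 vs 10/30 in the randomised patients) may well contribute.
- **No large systematic bias was shown.** Simulating from a true OR of 3.7, the median of finite pooled fits stayed near the truth (3.6 to 4.0). This stands too. The same simulation shows instability: non-finite mesh coefficients in 8–14% of randomised and 19–44% of observational fits.
- **Firth is a choice, and its Wald interval includes 1.** True. Profile limits are usual in sparse data, and the SAP's own per-study intervals reproduce as profile limits. The SAP's reason for its methods is audience familiarity, which is a real cost of changing.

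**Conclusion.** The concern holds. With about 1 to 2.4 events per slope, the adjusted pooled odds ratio of 12.5 cannot be relied on for size. The move from p=0.070 to p=0.012 does not identify confounding: crossing 0.05 happens in about half of datasets with the same counts and uninformative covariates, and a fifth of the log-OR shift is re-weighting. Sparse-data inflation, non-collapsibility, changed weights, chance imbalance and confounding in the observational patients all remain possible, and 12 and 8 events cannot separate them.

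The claim is not that the direction is wrong: the unadjusted randomised estimate favours Strattice, although its lower limit is close to 1 and depends on the interval method. Nor is it that 12.5 is pure artefact.

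The simulation figures rest on the tabled margins, independent covariates and the assumed codings. The trial's own penalised adjusted odds ratio cannot be computed without patient data.

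**What to change.** 1. State how wound class was coded.
2. Refit the adjusted models with Firth penalisation and penalised-profile intervals, with wound class collapsed or fewer covariates. The two-stage pooling can stay. The single propensity-score covariate described in the SAP's FAQ is an alternative, but in the observational patients the score would be estimated from 20 people with no immunosuppressed XenMatrix patient.
3. Beside it, report penalised or exact unadjusted results for the randomised patients (Firth OR 6.1, profile interval 1.2 to 60.6; Fisher p=0.035).
4. Delete the overfitting sentence in Primary Outcome Analysis, or replace it with: *The adjusted models have about 1 to 2.4 events per slope and are prone to overfitting.*
5. Replace the two Executive Summary sentences on the shift with: *The adjusted and unadjusted pooled results differ. With 12 and 8 events this shift cannot be separated from sparse-data bias, non-collapsibility and changed study weights; chance imbalance or confounding in the observational patients may contribute.*

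Cost: one re-run with a standard R package and a few sentences. The downsides are probably a less striking adjusted figure, coarser adjustment if wound class is collapsed, and a method less familiar to the intended readers.
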